#### Table 2: Use of analysis cohorts

| Analysis Item   | Analysis Cohort |
|---|-----------------|
| All baseline summaries (i.e.: demographic, medical history) | ITT             |
| Primary Objective   | ITT, PP         |
| Secondary Objective   | ITT, PP         |
| Adverse Event summary                                       | ITT             |
| Device Deficiency summary                                   | ITT             |
| Deviation summary   | ITT             |

Summaries for subjects enrolled but not in the ITT set can be presented if necessary.

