8.4.2. Reveal LINQ ICM Insertion

The insertion procedure must occur within 10 days of the qualifying stroke event and after randomization. The insertion will be performed in accordance with the hospital's standard insertion practice and in accordance with the Medtronic Reveal LINQ ICM insertion instructions which are found within the Reveal LINQ ICM Clinician manual. The following information is required to be collected at the insertion visit:

- System and Procedure Information
 - System and procedure details will be collected including, but not limited to procedure date, device serial number, location of insertion procedure, location/orientation of inserted device, antibiotic use, and closure method.
- Device Programming/Interrogation
 - Programming requirements for the Reveal LINQ ICM are outlined in Table 6 below. A full device interrogation will be collected after final programming. Programming changes will be allowed only when clinically necessary. All deviations from the programming guidelines (regardless of when they occur) must be documented on a Study Deviation e-CRF, including the rationale for the deviation.

18 December 2018 Version 4.0 Page 31 of 66

Table 3: Reveal LINQ ICM Programming

Parameter	Required Setting
Reason for Monitoring	Cryptogenic Stroke
AF Detection Sensitivity	Balanced Sensitivity
Ectopy Rejection	Aggressive
AT/AF Recording Threshold	All Episodes
Type of AT/AF Detection	AF Only
Wireless Data Priority	Tachy, Pause, Brady
Tachy Detection	ON
Brady Detection	ON
Pause Detection	ON

The subject will be instructed about the use of the Medtronic MyCareLink Monitor and the Patient Assistant.

If the subject does not have a Reveal LINQ ICM device in the body at the conclusion of the procedure, the subject should remain in the study and the follow-up schedule remains unchanged. For these patients, CareLink transmissions at 3 and 9 months are not required.

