# 6. Determination of Sample Size

### 6.1. Primary Objective

A total of 23 first events across the two treatment groups are required to demonstrate the primary objective of the study. Assuming 2% attrition from enrollment to randomization, approximately 486 subjects will be randomized. Subjects will be followed for 3 years, until end of device life or until official study closure, whichever occurs first. However, the primary objective of the study, upon which this sample size calculation is based, will be analyzed considering data up to the 12 months follow-up visit for all subjects in the study at the time of the analysis. This sample size calculation then assumes a follow-up time equal to 1 year and an accrual time equal to zero (data from all subjects is analyzed from randomization to the 12th month follow-up visit, regardless of how long they've been in the study at the time of the analysis). Withdrawn subjects will not be replaced.

The assumptions used for the calculations were:

- Two-sided log-rank test
- Alpha = 0.05
- 85% power
- Annual Attrition rate = 10% (in each treatment group)
- Annual Crossover rate = 5% (in each treatment group)
- Follow-up Time = 1 year
- Event-free one-year survival rate of 92% in the continuous monitoring arm
- Event-free one-year survival rate of 98% in the control arm (hazard ratio of 4.13)

This document is electronically controlled. Printed copies are considered uncontrolled.

Version 2.0 15/MAY/2017

The procedure "Logrank tests (Lakatos) using proportion surviving" in PASS 2008 was used to calculate the number of events required to test this objective.

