### 7.1.3. Analysis Sets

The following analysis sets will be used in this study:

This document is electronically controlled. Printed copies are considered uncontrolled.

Enrollment Cohort: All subjects who signed the informed consent and meet inclusion/exclusion criteria.

**Intent to Treat (ITT) Cohort:** Enrolled subjects who are randomized, according to the treatment arm to which they were randomized.

**Per Protocol (PP) Cohort:** All subjects who fulfill the protocol as follows:

- In ITT cohort (i.e., meets inclusion/exclusion criteria, gave informed consent, and was randomized)
- Exclude subjects that cross-over to the other arm
- Exclude subjects that are not programmed as follows at any point during the study (from CIP):
  - Reason for Monitoring = Cryptogenic Stroke
  - AF Detection Sensitivity = Balanced Sensitivity
  - Ectopy Rejection = Aggressive
  - AT/AF Recording Threshold = All Episodes
  - Type of AT/AF Detection = AF Only

The ITT Cohort will be used to analyze the primary and secondary objectives. The use of the PP Cohort will be specified in each evaluation objective.

Table 2 below shows the use of each analysis set:

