### 7.10. Safety Evaluation

Relatedness of adverse events using the CEC adjudication will be summarized using counts and percentages. Seriousness of adverse events using the Medtronic classification will be summarized using counts and percentages. Details of individual adverse events will be listed.

This document is electronically controlled. Printed copies are considered uncontrolled.

Version 2.0 15/MAY/2017

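### The SAP gives device and procedure adverse events and device deficiencies no device-recipient denominator: a modest reporting gap that is cheap to close

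*SAP*

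**What the plan says.** SAP Table 2 lists the "Adverse Event summary" and the "Device Deficiency summary" with ITT as the only cohort. SAP 7.1.3 defines that cohort as "Enrolled subjects who are randomized, according to the treatment arm to which they were randomized". The only other set formed after randomization is the per-protocol set. It has the rule "Exclude subjects that cross-over to the other arm" and is not assigned to any safety row.

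SAP 7.10 is short: "Relatedness of adverse events using the CEC adjudication will be summarized using counts and percentages". Seriousness is handled the same way, and "Details of individual adverse events will be listed". The section names no columns and no denominator. SAP 7.2 lets percentages be taken over patients or over events. SAP 7.7 does use a column of subjects who had the implant procedure, but only within the ICM arm and only for insertion and system-modification variables.

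The documents foresee both groups that make ITT awkward here:

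- SAP 6.1 and 6.2 plan for 5% annual crossover in each arm.
- Protocol 8.4.2 covers unsuccessful insertions, which do not end participation: "If the subject does not have a Reveal LINQ ICM device in the body at the conclusion of the procedure, the subject should remain". Protocol 8.3 keeps subjects in their assigned arm when the assigned approach is not feasible, so ICM-arm subjects with no attempted insertion can also exist. The documents give no number for either.

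**The concern.** Protocol Table 6 ties procedure-related events to implantation or modification of the LINQ system, and system-related events to the presence or performance of its components. A subject with no attempted insertion and no system is not at risk of them. ITT is the right basis for comparing AF detection. It is the wrong denominator for the risk per insertion or per device.

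Followed as written, the SAP yields a rate that depends on how many ICM-arm subjects went without a device. It gives no specified place where a control subject's LINQ insertion is counted among device recipients. The per-protocol set does not help. It removes crossovers instead of regrouping them, and Protocol 8.4.6 requires a crossover form when a LINQ is explanted, so some subjects who had a device problem could leave that set.

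At stake is how clearly the report states device and insertion risk in this population. Protocol 3.2 says the study supports bringing the ICM into this care pathway, so a per-recipient rate is a figure that readers will want.

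**Working it through.** The plan states no device-event rate, so there is no figure to reproduce. The arithmetic below only sizes the effect.

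**Inputs from the documents**
- About 486 randomized 1:1 (SAP 6.1 and 5.3.1): 486 / 2 = 243 per arm.
- Annual crossover 5% in each arm and annual attrition 10% (SAP 6.1, 6.2).
- Follow-up up to 3 years (SAP 6.1).

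**Assumptions, not in the documents**
- Every control crossover receives a LINQ (an upper bound).
- Share u of ICM-arm subjects never implanted: 0 to 10%.
- True device or procedure event rate p per recipient: 2% to 5%, the same in both arms.

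**Step 1. Control subjects with a device**, 243 × (1 − 0.95^t):
- 1 year: 243 × 0.05 = 12.2
- 3 years: 243 × (1 − 0.8574) = 34.7
- With attrition as a competing loss, 243 × [c / (c + l)] × [1 − (0.95 × 0.90)^t], where c = −ln 0.95 = 0.0513 and l = −ln 0.90 = 0.1054: 11.5 at 1 year and 29.8 at 3 years.

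**Step 2. Their share of all device recipients**, x / [x + 243(1 − u)]:

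| | u = 0 | u = 10% |
|---|---|---|
| 1 year (x = 12.2) | 4.8% | 5.3% |
| 3 years (x = 34.7) | 12.5% | 13.7% |

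Under equal risk per insertion, this is also the share of procedure-related events that would sit under control. For events that accrue over time the share would be smaller, because crossovers carry the device for less time.

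**Step 3. Tables by randomized arm**
- ICM-arm rate = p × (1 − u). A true 5% shows as 5.0% to 4.5%, and a true 2% as 2.0% to 1.8%.
- Control-arm device events = x × p. The range is 12.2 × 2% = 0.24 to 34.7 × 5% = 1.74 subjects, or 0.1% to 0.7% of 243.

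**Step 4. Tables pooled over 486**
- Rate shown = p × [243(1 − u) + x] / 486.
- If no crossover receives a LINQ (x = 0), the multiplier is 0.50 at u = 0 and 0.45 at u = 10%.
- At the upper bound (x = 34.7, u = 0) it is 277.7 / 486 = 0.57.
- A true 5% therefore shows as about 2.3% to 2.9%.

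Pooling removes the misplacement of crossovers' events but roughly halves the rate. If percentages are taken over events, as SAP 7.2 allows, the table gives no risk per subject at all.

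**The case against.** The strongest reply is that little turns on this. The only objectives are AF incidence through 12 months and over all follow-up. The device is market-released and used within its labeling, and Protocol section 9 treats its safety as already shown. SAP 7.10 is descriptive. Each reported event is classified for relation to system and procedure (Protocol Table 7), relatedness is summarized from CEC adjudication, events are listed individually, and crossovers are recorded as they occur. A LINQ-related event in a control subject would be recognizable as such. ITT includes everyone randomized, so none of their events is lost, and SAP section 3 expects analyses beyond the plan.

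Most of this stands, and it limits the point to reporting clarity. It does not remove it. A listing gives no rate, and a denominator chosen later in a non-blinded study analyzed by the sponsor is not pre-specified.

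A reader might go further in four ways that the documents do not support:

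- That safety tables certainly have arm columns. Arm grouping is only an inference from Table 2 and the ITT definition.
- That a between-arm safety contrast is biased toward no difference. The plan contains no such comparison.
- That per-device risk is the trial's main safety question. Nothing in either document says so.
- That Protocol 8.4.2 describes subjects who never had an insertion attempted. It concerns those without a device at the end of a procedure. They were at risk of procedure-related events and belong in that denominator.

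**Conclusion.** The point holds as a modest gap in descriptive safety reporting. Table 2 sets a rule, ITT only, that does not fit events arising solely from an insertion or a device, and no section supplies a per-recipient rate.

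Its size depends on the layout. By arm, the ICM-arm rate is multiplied by 1.00 to 0.90, and fewer than two control subjects with device events would be expected under the assumed rates. Pooled, the rate falls to about half.

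The counts of 12 and 35 control subjects are ceilings, not forecasts. The 5% rate is a power-calculation assumption, and the counts also need every crossover to receive a LINQ. The never-implanted share and the event rate are assumed as well. The primary and secondary analyses are not affected.

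**What to change.** In SAP Table 2 and 7.10, add a device set defined by the device actually received, in either arm:

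- Procedure-related adverse events: all subjects with an attempted LINQ insertion, followed from the attempt.
- System-related adverse events and device deficiencies: all subjects with a LINQ inserted, followed from insertion.
- Keep the ITT tables alongside, and state their columns and whether percentages are of subjects or of events.

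This is a cheap improvement: SAP wording, one more analysis set and one extra table set. Procedure dates (Protocol 8.4.2) and crossovers (Protocol Table 2) are already collected, and the current protocol collects device data from any subject with an ICM. One detail should be confirmed: that a failed attempt in a control subject is captured, since the device items in Protocol Table 2 apply to subjects with an ICM.

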### 7.2. General Methodology

Data summaries for categorical data will be summarized as count, e.g., number of patients, and/or number of events, and a percentage relative to the total number of patients/events. Continuous variables will be represented by mean, standard deviation, median and quartiles.

Time to event methods will be used for the primary and secondary objectives. P-values for hypothesis testing will be evaluated based on two-sided testing using a significance level of 0.05. Confidence intervals will be reported as two-sided 95% confidence intervals.

This document is electronically controlled. Printed copies are considered uncontrolled.

### 7.3. Center Pooling

The study is expected to be conducted in approximately 40 centers in the USA. The data from all centers will be pooled. There will be no minimum limit that each investigator must enroll. The maximum number of enrolled subjects per center is 50 subjects. In addition, a guidance was sent to sites stating that a maximum of 3 subjects with lacunar stroke (i.e. small vessel disease) may be enrolled at each site. This restriction is not in the CIP. Adjustment for center effect will not be included in statistical modeling.

## 7.4. Handling of Missing Data and Dropouts

The primary and secondary objectives use time to event methods, thus there will only be missing data for subjects with no follow-up time. Otherwise, each subject will have data to contribute to the analysis.

# 7.5. Adjustments for Multiple Comparisons

No adjustments for multiple comparisons will be made.

### 7.6. Demographic and Other Baseline Characteristics

Baseline variables such as demographics, physical examination, cardiac disease classification, testing results, qualifying stroke event, medications, modified rank scale, and NIH stroke scale information may be reported. Continuous variables will be reported as mean, standard deviation, median, minimum, maximum, and quartiles and categorical variables will be reported as number and percentage of subjects.

The summary tables will include a column for ITT treatment arm subjects, ITT control arm subjects, and all ITT subjects.

A summary table for subjects enrolled but not in the ITT cohort may be presented if necessary.

### 7.7. Treatment Characteristics

Treatment characteristic variables from the Insertion Procedure and System Modification CRFs will be reported. Continuous variables will be reported as mean, standard deviation, median, minimum, maximum, and guartiles. Categorical variables will be reported as number and percentage of subjects.

The summary tables will include a column for ITT treatment arm subjects who underwent the Reveal implant procedure.

### 7.8. Subgroup Analyses

### Stroke Subgroups

Subgroup analysis for subjects with small vessel disease stroke and large vessel cervical or intracranial atherosclerosis stroke will be presented.

The source data for defining the subgroups come from the question "TOAST Classification of Subtypes of Acute Ischemic Stroke" on the BASELINE CRF.

This document is electronically controlled. Printed copies are considered uncontrolled.

Version 2.0 15/MAY/2017

- If the CRF value is "Large-artery atherosclerosis", then the subject is in the "large vessel cervical or intracranial atherosclerosis" subgroup
- If the CRF value is "Small-vessel occlusion (lacune)", then the subject is in the "small vessel disease stroke" subgroup

Kaplan-Meier curves will be generated for each randomization arm in each subgroup.

A Cox proportional hazards model will be used to test the interaction using the Wald test between treatment and subgroup.

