5.1. Study Design

Stroke AF is a prospective, multi-site, randomized, controlled, non-blinded, post-market study. The Stroke AF study will compare the incidence rate of AF through 12 months between the continuous monitoring arm and the control arm in subjects with a recent ischemic stroke of presumed known origin. Once enrolled, subjects will be randomized 1:1 (continuous monitoring vs control). Subjects randomized to the continuous monitoring arm will have a Reveal LINQ ICM inserted within 10 days of the qualifying stroke and undergo continuous remote monitoring. Subjects randomized to the control arm will be followed per site specific standard of care.

The study is expected to be conducted at approximately 40 sites located in the United States (U.S.).

It is estimated that approximately 496 subjects will be enrolled in the study. Assuming 2% attrition from enrollment to randomization, approximately 486 subjects will have randomized. A total of 23 first documented AF events within 12 months of randomization are required for the study to test the primary objective. AF will be defined as an AF event lasting more than 30 seconds and adjudicated by the endpoint adjudication committee. The analysis of the primary objective will occur after all enrolled subjects have completed 12 months of follow-up. Approximately 248 devices may be used in the study. Based on previous studies of this scope and magnitude, it is estimated that sites may identify and enroll on average one eligible subject per month.

To ensure a widespread distribution of data and minimize site bias in study results, the maximum number of subjects who may be enrolled at a single site is 50 subjects. Sites that enroll faster than others will be allowed to do so in order to maintain an adequate overall study enrollment rate. In addition, to ensure a robust dataset is available for subgroup analysis, a maximum of 50% (approximately248) subjects with lacunar stroke (i.e., small vessel disease) may be enrolled. Medtronic will notify study sites when enrollment of lacunar stroke subjects is no longer allowed, if applicable.

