### 6.2. Secondary Objective

A number of 486 subjects randomized to achieve the primary objective and the assumptions below will also ensure 100% power to test the **secondary objective** of the study.

The assumptions used for the calculations were:

- Two-sided log-rank test
- Alpha = 0.05
- Annual Attrition rate = 10% (in each treatment group)
- Annual Crossover rate = 5% (in each treatment group)
- Accrual Time = 2 years
- Follow-up Time = 3 years
- Event-free survival rate of 80% in the continuous monitoring arm
- Event-free survival rate of 97% in the control arm (hazard ratio of 7.33)

The procedure "Logrank tests (Lakatos) using proportion surviving" in PASS 2008 was used to calculate the power to test this objective.

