### vi. Subgroup Analyses

Subgroup analysis for subjects with small vessel disease stroke and large vessel cervical or intracranial atherosclerosis stroke will be presented. See section 7.9 for details.

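### The Cox Wald test of treatment by stroke subtype has no rule for an arm-by-subtype cell without events, which is expected in about 16% of 12-month analyses

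*SAP*

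**What the plan says.** SAP 7.8 (Stroke Subgroups) assigns subjects to small-vessel or large-vessel subgroups from the baseline TOAST item. It asks for Kaplan-Meier curves by arm in each subgroup and then states: "A Cox proportional hazards model will be used to test the interaction using the Wald test between treatment and subgroup".

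SAP 7.9 applies this to both objectives. Under the primary and again under the secondary objective it says "Subgroup analysis for subjects with small vessel disease stroke and large vessel cervical or intracranial atherosclerosis stroke will be presented". Both places refer to 7.9 for details that are actually in 7.8.

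The figures that fix the expected event counts are in SAP 6:

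- **12 months (6.1):** 92% event-free in the monitoring arm, and "Event-free one-year survival rate of 98% in the control arm (hazard ratio of 4.13"), with 10% annual attrition and 5% annual crossover in each arm and about 486 randomized. The event target is: "A total of 23 first events across the two treatment groups are required to demonstrate the primary objective of the study".
- **Full follow-up (6.2):** 80% event-free in the monitoring arm, and "Event-free survival rate of 97% in the control arm (hazard ratio of 7.33"), with the same attrition and crossover.

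On the lacunar share, Protocol 5.1 says "a maximum of 50% (approximately248) subjects with lacunar stroke (i.e., small vessel disease) may be enrolled" and gives subgroup analysis as the reason. SAP 7.3 reports site guidance that "a maximum of 3 subjects with lacunar stroke (i.e. small vessel disease) may be enrolled at each site", and notes that it is not in the protocol.

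Neither document gives a minimum event count, a rule for a cell with no events, or a penalized, exact or likelihood-ratio alternative. SAP 7.4 deals only with subjects who have no follow-up. SAP 7.12 allows further exploratory analyses and changes justified in the report.

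**The concern.** A Wald test divides the estimated interaction by its standard error. If one of the four arm-by-subtype cells has no event, the partial likelihood has no finite maximum for the interaction. The coefficient and its standard error grow together, and the software stops or prints a p-value near 1. The most extreme pattern in the data can therefore give the least significant result. With only one or two events in a cell the estimate is finite, but the standard error is large and the test is conservative.

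At stake is the one formal comparison of effect between stroke types, for which the protocol restricts lacunar enrolment. A p-value near 1 could be read as evidence that the effect is the same in both types. A replacement test chosen after the failure would be post hoc, in a non-blinded trial analysed by the sponsor.

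**Working it through.** **1. The plan's own figures.** Hazard ratio: ln(0.92)/ln(0.98) = 4.13, as stated. A Lakatos calculation gives 23.7 required events without crossover, in line with the stated 23. Modelling two-way crossover as a switch of hazard gives about 26, which does not bear on this point. The expected count at 486 randomized, below, is 23.1.

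**2. Expected events by arm at 12 months (243 per arm).** Annual hazards:

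- AF: control −ln(0.98) = 0.0202; monitoring −ln(0.92) = 0.0834
- attrition: δ = −ln(0.90) = 0.1054
- crossover: γ = −ln(0.95) = 0.0513

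For an arm with AF hazard λ, and hazard λ′ after crossover, let a = λ+δ+γ, b = λ′+δ and f(x) = (1−e^(−x))/x. Then

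P(event) = λ f(a) + λ′ γ [f(b) − f(a)]/(a − b).

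- Control: 0.02041 × 243 = 4.96
- Monitoring: 0.07459 × 243 = 18.1
- Total: 23.1

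**3. Chance of an empty cell.** Assume equal AF rates in both subtypes, every subject in one of them, and lacunar share s in both arms. With Poisson counts,

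P(any empty) = 1 − Π(1 − e^(−m)), over cell means m = 4.96s, 4.96(1−s), 18.1s, 18.1(1−s).

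At s = 0.5 each control cell expects 2.48 events and e^(−2.48) = 0.084. The monitoring cells are almost never empty. So P = 1 − (1 − 0.084)² = 0.161.

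| Lacunar share | 12 months | Full follow-up |
|---|---|---|
| 50% | 16.1% | 2.4% |
| 40% | 18.2% | 3.5% |
| 25% | 31.4% | 11.2% |

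The last column uses the 6.2 assumptions: 39.5 monitoring and 8.8 control events over 36 months. The 25% row applies only if the site guidance stayed in force (3 × 40 = 120 of 486, or 24.7%).

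Binomial counts at 50% give 16.4% with no losses, 15.7% with attrition and crossover, and 18.5% with attrition only. At 50%, some control cell has 0 or 1 event with probability 1 − [1 − e^(−2.48)(1 + 2.48)]² = 0.50.

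**4. The Wald test when no cell is empty.** With monitoring events a₁, a₂ and control events c₁, c₂ in the two subtypes, approximately

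z = ln[(a₁/c₁)/(a₂/c₂)] / √(1/a₁ + 1/c₁ + 1/a₂ + 1/c₂).

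Take 9 and 9 monitoring events and 5 control events:

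- split 3:2: z = 0.405/1.027, p = 0.69
- split 4:1: z = 1.386/1.213, p = 0.25
- split 5:0: no finite estimate, p near 1

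No split reaches 0.05.

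**5. Size under no interaction, 12 months (nominal 5%), 400,000 Poisson draws.**

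| Lacunar share | Wald, no empty cell | Wald, all trials | Firth penalized LR, all trials |
|---|---|---|---|
| 50% | 1.25% | 1.0% | 3.6% |
| 40% | 1.47% | 1.2% | 3.4% |
| 25% | 2.10% | 1.4% | 3.0% |

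The third column counts an empty cell as no rejection, for example 1.25% × (1 − 0.161) = 1.0%. As a check, 5,000 simulated patient-level trials with Cox fits gave, at 50/40/25%, empty cells in 15.2/17.6/32.4%, Wald size without empty cells of 1.2/1.6/1.8%, and Cox-Firth size of 3.8/3.5/2.8%. The ordinary likelihood-ratio test runs to about 7%.

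**6. Illustrative power.** The subtype hazard ratios are assumptions, not in the documents. Empty-cell trials count as Wald non-rejections.

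| Assumed HR, lacunar v large-vessel (50/50) | Wald | Firth |
|---|---|---|
| 1 v 8, plan's attrition and crossover | 25% | 38% |
| 2 v 6, about 5 control events | 11% | 18% |
| 3 v 6, about 5 control events | 5% | 10% |

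**The case against.** The strongest reply is that this test decides nothing. Success rests on the intention-to-treat log-rank test, the study is powered for that alone, and subgroup results are only to be presented. A conservative test creates no false subgroup claims, and the required Kaplan-Meier curves would show an empty cell as a flat line. All of this stands and limits the weight of the point.

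Second, the real limit is about 5 control events, not the Wald statistic. This also stands: with milder interactions both tests have little power. It does not defend a statistic that can give its weakest result for the most extreme pattern.

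Third, some figures depend on conditions the documents do not settle. The 31% needs the 3-per-site guidance to have continued, while the current protocol sets a 50% maximum. The documents give no subtype-specific AF rates, so the 16% is conditional on equal rates. At full follow-up the problem is small at 40% to 50% lacunar. These are fair limits, but the 12-month result at the protocol's own cap does not depend on the guidance.

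Fourth, a fallback used only for empty cells would be narrower. It would leave the conservative Wald test in all other trials and make the choice of test depend on the data. The choice of method does matter: with 9 v 5 events in one subtype and 9 v 0 in the other, Cox-Firth gives a median p of 0.047 over random event orders and Fisher's exact test 0.12. That is a reason to fix the method in advance.

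**Conclusion.** The point holds. Followed as written, SAP 7.8 gives no usable interaction p-value in about one 12-month analysis in six, and a markedly conservative one otherwise. The size is 16% empty cells at a 50% lacunar share and 18% at 40%, with Wald size of 1.2% to 1.5% when every cell has an event. At full follow-up, empty cells fall to about 2% to 4% at those shares.

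These figures rest on the plan's event rates, attrition and crossover, equal AF rates in both subtypes, and an even split of subtypes across arms. Under equal rates a 50% share is close to the most favourable case, so a lower lacunar share makes matters worse. The primary and secondary log-rank tests are untouched. This is a worthwhile, low-cost improvement to a supportive analysis.

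**What to change.** In SAP 7.8, replace the Wald sentence with text to this effect:

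*The treatment-by-subgroup interaction will be tested in a Firth penalized-likelihood Cox model by the penalized likelihood-ratio test, with profile-likelihood 95% confidence intervals for the hazard ratio in each subgroup, in both the 12-month and full-follow-up analyses, whatever the observed event counts.*

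Add that a non-significant result does not show a uniform effect, because the test remains underpowered.

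An exact conditional test would also close the gap but is more conservative. The ordinary likelihood-ratio test is not a good substitute because its size exceeds 5% at these counts.

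The cost is one or two SAP sentences and a standard software option, with slight shrinkage of the subgroup estimates. No new data are needed and the primary analysis does not change. The cross-references in SAP 7.9 can be corrected to 7.8 in the same edit.
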